1.1.4. Rationale for combining Rituximab with Ibrutinib for the treatment of cGVHD

The clinical efficacy of rituximab has provided compelling evidence that B cells play an important role in human cGVHD, but the mechanisms that promote and sustain B-cell involvement remain poorly studied. The durability of clinical responses to rituximab in patients with cGVHD remains unclear (Cutler, Miklos et al. 2006; Zaja, Bacigalupo et al. 2007). In patients with autoimmune diseases, initial clinical responses to rituximab are inevitably followed by clinical relapse in the majority of patients. Thus, although clinical responses to rituximab are compelling, incomplete elimination of potentially autoreactive B cells may lead to cGVHD recurrence. Therefore, there is a rationale for combining CD20-targeting antibodies with B cell signaling inhibitors in the hopes of improving the efficacy and durability of the response.

The combination of Rituximab and Ibrutinib has been used successfully to treat patients with chronic lymphocytic leukemia (Burger, Keating et al. 2014) and mantle cell lymphoma (Wang, Lee et al. 2016), demonstrating safety for this combination.

1.2. Ibrutinib Overview

Ibrutinib (IMBRUVICA®) is a first-in-class, potent, orally administered, covalently binding inhibitor of Bruton's tyrosine kinase (BTK) co-developed by Pharmacyclics LLC and Janssen Research & Development LLC for the treatment of B-cell malignancies.

Ibrutinib has been approved in over 80 countries, including the United States (US) and European Union (EU), for indications covering the treatment of patients with mantle cell lymphoma (MCL) who have received at least 1 prior therapy, patients with chronic lymphocytic leukemia (CLL)/small lymphocytic lymphoma (SLL), including CLL/SLL with a deletion of the short arm of chromosome 17 (del17p), patients with Waldenström's macroglobulinemia (WM), patients with Marginal Zone Lymphoma (MZL) who require systemic therapy and have received at least one prior anti-CD20-based therapy, and adult patients with cGVHD after failure of 1 or more

lines of systemic therapy. For the most up to date and comprehensive nonclinical and clinical information regarding ibrutinib background, safety, in vitro and in vivo preclinical activity, pharmacokinetics, and toxicology of ibrutinib, always refer to the latest version of the [ibrutinib Investigator's Brochure \(IB\)](#) and/or the applicable regional labeling information.

1.2.1. Risks

1.2.1.1. Bleeding-related Events

There have been reports of hemorrhagic events in subjects treated with ibrutinib, both with and without thrombocytopenia. These include minor hemorrhagic events such as contusion, epistaxis, and petechiae; and major hemorrhagic events, some fatal, including gastrointestinal bleeding, intracranial hemorrhage, and hematuria.

Initially, subjects were excluded from participation in specific ibrutinib Phase 2 and 3 studies if they required warfarin or other vitamin K antagonists. Warfarin or other vitamin K antagonists should not be administered concomitantly with ibrutinib unless specified in the protocol.

Supplements such as fish oil and vitamin E preparations should be avoided. In an in vitro platelet function study, inhibitory effects of ibrutinib on collagen-induced platelet aggregation were observed, refer to [Section 6.2.3](#). Use of ibrutinib in subjects requiring other anticoagulants or medications that inhibit platelet function may increase the risk of bleeding. See [Section 6.2.3](#) for guidance on concomitant use of anticoagulants, antiplatelet therapy and/or supplements.

Ibrutinib should be held at least 3 to 7 days pre- and post-surgery, depending upon the type of surgery and the risk of bleeding. See [Section 6.4](#) for guidance on ibrutinib management with surgeries or procedures. Patients with congenital bleeding diathesis have not been studied.

1.2.1.2. Infections

Infections (including sepsis, bacterial, viral, or fungal infections) were observed in subjects treated with ibrutinib. Some of these infections have been associated with hospitalization and death. Consider prophylaxis according to standard of care in subjects who are at increased risk for opportunistic infections (reference [Section 6.1](#)). Although causality has not been established, cases of progressive multifocal leukoencephalopathy (PML) and hepatitis B reactivation have occurred in subjects treated with ibrutinib. Subjects should be monitored for signs and symptoms (fever, chills, weakness, confusion, vomiting and jaundice) and appropriate therapy should be instituted as indicated.

1.2.1.3. Cytopenias

Treatment-emergent Grade 3 or 4 cytopenias (neutropenia, thrombocytopenia, and anemia) were reported in subjects treated with ibrutinib. Monitor complete blood counts monthly.

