3. STUDY DESIGN

3.1. Overview of Study Design

The rationale for the study concept is provided in [Section 1.3](#).

This is a phase II trial evaluating the safety and efficacy of the combination of Ibrutinib and Rituximab as primary treatment of cGVHD. We plan to enroll 35 patients on this study. Patients will be formally monitored monthly for 12 months to evaluate for outcome and safety endpoints. All other assessments will be done at the physician's discretion or institutional standards. All patients, responders and treatment failures, will be followed for a period of one year from the time of initiation of therapy. The primary endpoint will be the proportion of patients that are alive and off all systemic IST at 12 months following initiation of treatment.

Eligible patients will be those with a first episode of symptomatic cGVHD, requiring systemic immunosuppression for control of symptoms. Following study entry, patients will be started on:

[figure not shown]
1. Ibrutinib 420mg PO QDAY (28-day cycles) for a total of 12 cycles unless discontinued early due to toxicity (see stopping rules in section 5.1.1.4). Dose adjustments are required for patients with hepatic impairment or those receiving concomitant voriconazole or posaconazole or other strong CyP 3A4 inhibitor according to sections 5.1.1.5 and 5.1.1.6.
2. Rituximab 375mg/m² IV weekly x 4 weeks (to be started on study day 7 ± 3 days), then 375mg/m² IV q3months x 4 doses (months 4, 7, 10, 13).

Additional cGVHD treatment will include:

- **Sirolimus** (target level 4-10 ng/mL) – patients currently receiving a calcineurin inhibitor (tacrolimus or cyclosporine) and/or mycophenolate mofetil for GVHD prophylaxis will be converted to sirolimus per institutional guidelines. In the case of contraindication or intolerance to sirolimus, another systemic immunosuppressive (IS) drug (i.e. tacrolimus or cyclosporine) may be substituted at the discretion of the treating investigator.
- Short-course corticosteroids may be used, if necessary, for more rapid symptom control (≤1mg/kg Medrol, with planned taper to be completed no longer than 4 weeks).

When cGVHD manifestations have been quiescent for at least 4 weeks, sirolimus (or other IS medication) should be tapered over 4 weeks or per investigator discretion.

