7.2. Efficacy Evaluations

Formal efficacy assessments will be performed at baseline and post-treatment, monthly x 3 (1, 2, and 3 months), then q3months x 3 (6, 9, and 12 months). See section 8.2.2 for detailed study assessments. All other assessments will be done at the physician's discretion or institutional standards.

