8.2.2. Response Follow-up

Required testing for the response follow-up visits (months 1, 2, 3, 6, 9, 12):

- Medical history
- Physical examination, including vital signs, weight, and Karnofsky performance status
- Laboratory evaluation per institutional guidelines including CBC with differential, glucose, BUN, creatinine, total bilirubin, alkaline phosphatase, LDH, albumin, SGOT(AST), SGPT (ALT), CRP, CK, calcium, and magnesium.
- Biomarkers (correlative lab studies)
- Documentation of concomitant medications
- Completion of institutional GVHD assessment form (see Appendix E)
- Completion of a GVHD patient self-report form (see Appendix F)
- Document cumulative corticosteroid use
- Document any new systemic IST and reason for use

- Document treatment-emergent toxicities and adverse events
- Document any IVIG use
- PFTs (at 3, 6, 9 and 12 month visits only)

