10.4. Efficacy Analysis Methods

This is a phase II trial evaluating the safety and efficacy of ibrutinib and rituximab as primary treatment of cGVHD. Efficacy and safety endpoints will be estimated according to the cumulative incidence and Kaplan-Meier methodology in the presence of competing risks. Outcomes will be compared to historical values based on the Gray's test and log rank test respectively. We plan to enroll 35 patients on this study. Patients will be formally monitored for 12 months to evaluate for outcome and safety endpoints (efficacy/safety visits at the completion of month 1, 2, 3, 6, 9, and 12). All other assessments will be done at the physician's discretion or institutional standards. All patients, responders and treatment failures, will be followed for a period of one year. The primary outcome measure will be the proportion of patients that are alive and off all systemic immunosuppression at 12 months following initiation of treatment. The primary endpoint will be estimated according to the Kaplan-Meier methodology in the presence of competing risks. Outcome will be compared to historical values based on the log rank test. Secondary outcome measures will be cGVHD response, cumulative steroid exposure, time to discontinuation of systemic immunosuppression, requirement for second-line cGVHD therapy, non-relapse and overall mortality, failure-free survival and safety. Secondary survival endpoints will be estimated according to the Kaplan-Meier methodology in the presence of competing risks, and outcomes will be compared to historical values based on the log rank test. Secondary time-to-event endpoints will be estimated according to cumulative incidence methodology, and outcomes will be compared to historical values based on the Gray's test (Gray 1988).

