14. APPENDICES

Appendix A. Schedule of Assessments

Study Day	Screening (within 7 days)	Day 1	Day 7 (+/- 3 days)	Month 1 (+/- 7 days)	Month 2 (+/- 7 days)	Month 3 (+/- 7 days)	Month 6 (+/- 7 days)	Month 9 (+/- 7 days)	Month 12 (+/- 7 days)
Informed Consent	X								
Eligibility Confirmation	X								
Ibrutinib 420mg daily ¹		X		Continuous daily dosing Dispensed on D1 of each cycle through Cycle 12					
Rituximab 375mg/m ²			X ²					X ³	
Medical History	X			X	X	X	X	X	X
Physical Exam w/vitals	X			X	X	X	X	X	X
Schirmer's test	X			X	X	X	X	X	X
Karnofsky Performance Status	X								
Serum Pregnancy	X								
Hepatitis serologies	X								
Fasting Lipid Panel	X								
CBC w/differential	X	X	X	X	X	X	X	X	X
Comprehensive Metabolic Panel ⁴	X	X	X	X	X	X	X	X	X
IgG level	X					X	X	X	X
CRP	X			X	X	X	X	X	X
CK	X			X	X	X	X	X	X
LDH	X			X	X	X	X	X	X
Biomarkers (Correlative studies)	X			X	X	X	X	X	X
Concomitant Medications	X			X	X	X	X	X	X
GVHD assessment ⁵	X			X	X	X	X	X	X
GVHD patient self-report form ⁶	X			X	X	X	X	X	X
Pulmonary Function Test	X					X	X	X	X
Calculate cumulative steroid dose				X	X	X	X	X	X
Any new systemic IST				X	X	X	X	X	X
Any IVIG therapy				X	X	X	X	X	X
Adverse Event				X	X	X	X	X	X

¹Dose reduction required when using strong Cyp 3A4 inhibitors (e.g. voriconazole or posaconazole, see Section 6.2.1, table 4) or with hepatic impairment (see Section 5.1.1.5, table 3).

²Rituximab induction 375mg/m² Q7days x 4 doses.

³Rituximab maintenance 375mg/m² q 3months (+/-7days) x 4 doses.

⁴Glucose, BUN, creatinine, total bilirubin, alkaline phosphatase, albumin, SGOT (AST), SGPT (ALT), calcium, magnesium

⁵See appendix E

⁶See appendix F

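### Two sections call for monthly blood counts and monthly formal monitoring, but the visit schedule requires neither at months 4, 5, 7, 8, 10 and 11

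*Combined protocol and SAP*

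**What the plan says.** Two places say monthly. Section 1.2.1.3 (Cytopenias), after reporting Grade 3 or 4 cytopenias on ibrutinib, instructs: "Monitor complete blood counts monthly". Section 3.1 (Overview of Study Design) says: "Patients will be formally monitored monthly for 12 months to evaluate for outcome and safety endpoints".

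Four places set a sparser schedule:

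- Section 7.2 has formal efficacy assessments "monthly x 3 (1, 2, and 3 months), then q3months x 3 (6, 9, and 12 months".
- Section 8.2.2 is headed "Required testing for the response follow-up visits (months 1, 2, 3, 6, 9, 12", and its list of required tests includes a blood count with differential.
- Section 10.4 refers to "efficacy/safety visits at the completion of month 1, 2, 3, 6, 9, and 12".
- Appendix A marks the row "CBC w/differential" at Screening, Day 1, Day 7 and months 1, 2, 3, 6, 9 and 12. It has no column for any other month.

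Appendix A also shows ibrutinib as "Dispensed on D1 of each cycle through Cycle 12", so patients receive drug every 28 days. Sections 3.1, 7.2 and 10.4 leave other assessments to the physician or to local practice, and Section 7.1.2 has laboratory work follow institutional guidelines.

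**The concern.** A site that follows Appendix A exactly does not meet the instruction in 1.2.1.3 or the statement in 3.1. A site that follows those two sections performs counts for which the schedule has no place.

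The difference has consequences because Section 5.1.1.4 makes ibrutinib changes mandatory on count results: Grade 4 thrombocytopenia (platelets below 25,000/µL), and Grade 4 neutropenia (ANC below 500/µL) lasting more than 7 days. Section 4.1 admits patients with platelets of 30 × 10⁹/L, close to the platelet trigger. A rule of this kind can only be applied when a count is taken.

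The safety endpoint in 10.2.2 is the incidence of related adverse events of Grade 3 or higher, and Section 7.1.1.5 requires every Grade 4 event to be recorded. A symptomless Grade 4 cytopenia that arises and resolves between required counts could be missed. Patients with more or fewer discretionary counts would also have different chances of an event being found.

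**Working it through.** The plan states no figure to reproduce, so the check compares the two sets of sections and counts months and intervals.

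**Inputs**

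- Monthly rule: 1.2.1.3 (blood counts) and 3.1 (formal monitoring), months 1 to 12.
- Scheduled follow-up counts: 8.2.2 and Appendix A, months 1, 2, 3, 6, 9, 12. Sections 7.2 and 10.4 give the same visits.
- Early counts: Appendix A, Screening, Day 1, Day 7.
- Visit window: Appendix A, ±7 days at each monthly or quarterly visit.
- Length of a month: not defined. I use 28 days (the cycle length in 3.1) and 30.4 days (calendar average) as the range.

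**Months without a required count**

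Removing {1, 2, 3, 6, 9, 12} from {1, …, 12} leaves {4, 5, 7, 8, 10, 11}. That is 6 of 12 months. A monthly rule gives 12 follow-up counts, and the schedule requires 6.

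**Interval between required counts**

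Nominal interval = months between visits × days per month. Longest interval allowed = nominal + 7 + 7, with the first visit early and the next one late.

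| Interval | Nominal, 28-day month | Nominal, 30.4-day month | Longest with windows |
|---|---|---|---|
| Months 1–2, 2–3 | 28 days | 30.4 days | 42 to about 44 days |
| Months 3–6, 6–9, 9–12 | 3 × 28 = 84 days | 3 × 30.4 = 91 days | 84 + 14 = 98 to 91 + 14 = 105 days |

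**Set against the dose rules**

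- Platelets: the entry floor is 30 × 10⁹/L and the Grade 4 trigger is 25 × 10⁹/L (25,000/µL), a margin of 30 − 25 = 5 × 10⁹/L. One count below the trigger is enough to apply the rule, so count spacing bears on it directly.
- Neutrophils: the trigger needs ANC below 500/µL for more than 7 days. One count cannot show duration, whether counts are monthly or quarterly. Spacing affects when a low value is first seen and repeat counts can start.

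**Set against event recording**

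Under 7.1.1.5, a Grade 3 event without hospitalization is recorded only if it is both unexpected and related. All Grade 4 and 5 events are recorded. Section 1.2.1.3 says Grade 3 or 4 cytopenias are already reported with ibrutinib, so a Grade 3 cytopenia is probably expected as 11.2 uses the term. Such an event without hospitalization would go unrecorded at any count frequency. What the schedule can lose is therefore mainly Grade 4.

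**Contacts in the months without a required count**

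Ibrutinib is dispensed on Day 1 of every cycle, and 3.1 places rituximab infusions at months 4, 7 and 10, three of the six months. Sections 8.2.1.1 and 8.2.2 and Appendix A tie no count to any of these contacts after the Day 1 and Day 7 counts.

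**The case against.** The strongest reply is that absence from the table does not mean absence of testing. Section 7.1.2 has laboratory work, including the blood count, follow institutional guidelines, other assessments are left to physician judgement, and patients attend for dispensing and infusions. This stands as a limit on the size of the point: 84 to 105 days is the gap between counts the protocol requires. A reader might infer that patients go unmonitored for a quarter, and the documents do not support that. But these provisions permit extra counts without requiring them, so they leave the conflict unresolved. In 3.1 the clause on other assessments comes straight after the sentence promising monthly formal monitoring, so it cannot be read as cancelling that sentence.

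A second reply is that the word monthly in 3.1 may be a slip, since the synopsis and 10.4 carry nearly the same sentence without it, and that 1.2.1.3 can be read as adding to the response visits. Either may be true. On the first reading 3.1 needs correcting; on the second Appendix A is incomplete. The text has to change in both cases.

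Two further inferences go too far. One is that the schedule makes the safety endpoint miss Grade 3 cytopenias generally; the recording rule in 7.1.1.5 already leaves out expected ones without hospitalization. The other is that monthly counts would make the neutropenia rule workable; a monthly count cannot establish a duration of more than 7 days either. It is also fair to say that the weeks just after entry, when a low starting platelet count is freshest, are the most densely sampled.

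**Conclusion.** The inconsistency is real, sits in current text and should be corrected. Sections 1.2.1.3 and 3.1 cannot both be met by following 7.2, 8.2.2, 10.4 and Appendix A. Six of 12 months have no required count, and required counts after month 3 are about 84 to 91 days apart, or up to about 98 to 105 days with the windows. The consequence falls mainly on the Grade 4 thrombocytopenia dose rule, on first detection of Grade 4 neutropenia, and on capture of symptomless Grade 4 cytopenias.

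This rests on three assumptions. A month is 28 to 30.4 days. Cytopenias count as expected events; the Investigator's Brochure that decides this is not part of the documents. And 7.1.1.5 governs what enters the case report form: 11.4.1 is worded more broadly, and if it governed, Grade 3 events would be affected too. How often counts would actually be taken between visits is unknown, so the number of missed events cannot be estimated.

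**What to change.** Reconcile 1.2.1.3 and 3.1 with 7.2, 8.2.2, 10.4 and Appendix A, so that one frequency for blood counts and one for formal monitoring apply throughout. Which frequency stands is for the sponsor to decide; this review takes no position. If counts and formal monitoring visits are meant to run at different frequencies, the protocol should say so.

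The cost is wording changes in those sections. If monthly stands, Appendix A also needs something for months 4, 5, 7, 8, 10 and 11, for which it has no columns: either added time points, or a footnote tying a blood count to the Day 1 dispensing that already takes place each cycle. The footnote would cover counts only. Monthly formal monitoring would also mean changing the visit lists in 7.2, 8.2.2 and 10.4. Sample size and the primary analysis are not affected.

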1.2.1.4. Interstitial Lung Disease (ILD)

Cases of interstitial lung disease (ILD) have been reported in subjects treated with ibrutinib. Monitor subjects for pulmonary symptoms indicative of ILD. If symptoms develop, interrupt ibrutinib and manage ILD appropriately. If symptoms persist, consider the risks and benefits of ibrutinib treatment and follow the protocol dose modification guidelines as needed (see [Section 5.1.1.4](#)).

1.2.1.5. Cardiac Arrhythmias

Atrial fibrillation, atrial flutter, and cases of ventricular tachyarrhythmia including some fatal events, have been reported in subjects treated with ibrutinib, particularly in subjects with cardiac risk factors, hypertension, acute infections, and a previous history of cardiac arrhythmia. Periodically monitor subjects clinically for cardiac arrhythmia. Subjects who develop arrhythmic symptoms (e.g., palpitations, lightheadedness, syncope, chest discomfort or new onset of dyspnea) should be evaluated clinically, and if indicated, have an ECG performed. For cardiac arrhythmias which persist, consider the risks and benefits of ibrutinib treatment and follow the protocol dose modification guidelines (see [Section 5.1.1.4](#)).

1.2.1.6. Tumor Lysis Syndrome

Tumor lysis syndrome has been reported with ibrutinib therapy. Subjects at risk of tumor lysis syndrome are those with high tumor burden prior to treatment. Monitor subjects closely and take appropriate precautions.

1.2.1.7. Non-melanoma Skin Cancer

Non-melanoma skin cancers have occurred in subjects treated with ibrutinib. Monitor subjects for the appearance of non-melanoma skin cancer.

1.2.1.8. Diarrhea

Diarrhea is the most frequently reported non-hematologic AE with ibrutinib monotherapy and combination therapy. Other frequently reported gastrointestinal events include nausea, vomiting, and constipation. These events are rarely severe and are generally managed with supportive therapies including antidiarrheals and antiemetics. Subjects should be monitored carefully for gastrointestinal AEs and cautioned to maintain fluid intake to avoid dehydration. Medical evaluation should be made to rule out other etiologies such as *Clostridium difficile* or other infectious agents. Should symptoms be severe or prolonged follow the protocol dose modification guidelines (see [Section 5.1.1.4](#)).

1.2.1.9. Rash

Rash has been commonly reported in subjects treated with either single agent ibrutinib or in combination with chemotherapy. Most rashes were mild to moderate in severity. Isolated cases

of severe cutaneous adverse reactions (SCARs) including Stevens-Johnson syndrome (SJS) have been reported in subjects treated with ibrutinib. Subjects should be closely monitored for signs and symptoms suggestive of SCAR including SJS. Subjects receiving ibrutinib should be observed closely for rashes and treated symptomatically, including interruption of the suspected agent as appropriate. In addition, hypersensitivity-related events including erythema, urticaria, and angioedema have been reported.

1.2.1.10. Hypertension

Hypertension has been commonly reported in subjects treated with ibrutinib. Monitor subjects for new onset of hypertension or hypertension that is not adequately controlled after starting ibrutinib. Adjust existing anti-hypertensive medications and/or initiate anti-hypertensive treatment as appropriate.

1.3. Study Rationale

Despite the importance of cGVHD as a major cause of morbidity and mortality following allogeneic transplant, therapies for this common post-transplant complication remain inadequate. Standard initial therapy of cGVHD is based on prolonged use of corticosteroids and a calcineurin inhibitor and has not changed for over 3 decades, despite limited efficacy and long-term toxicity. New treatments are clearly needed.

There is now considerable evidence from animal and human studies implicating B cells as an important player in the pathophysiology of cGVHD. This is best exemplified by the efficacy of both Rituximab (anti-CD20 B cell depleting antibody) and Ibrutinib (BTK inhibitor effecting B cell signaling) in the treatment of steroid-refractory cGVHD.

Given the effectiveness and favorable safety profile of both Rituximab and Ibrutinib in the steroid-refractory cGVHD patients, it is natural to study these agents in the upfront cGVHD setting. Rituximab has been studied in the upfront treatment of cGVHD in two recently published phase II studies, showing efficacy as a steroid-sparing agent with relatively low toxicity. We have previously shown that upfront Rituximab therapy can reduce the time to discontinuation of systemic immunosuppression, while limiting a patient's cumulative exposure to corticosteroids.

We hypothesize that combined CD20- and BTK-targeted B cell depleting therapy (BCDT) with Rituximab and Ibrutinib in the primary treatment of extensive cGVHD will produce quicker, better and more durable responses and improve outcomes in patients with cGVHD. The combination of Rituximab and Ibrutinib has been used successfully to treat patients with chronic lymphocytic leukemia (Burger, Keating et al. 2014) and mantle cell lymphoma (Wang, Lee et al. 2016), demonstrating safety for this combination.

